#### **Chemistry**

BUN/urea, creatinine, total bilirubin, direct bilirubin, aspartate aminotransferase (AST), alanine aminotransferase (ALT), alkaline phosphatase, gamma-glutamyl transpeptidase, lactate dehydrogenase, sodium, potassium, chloride, calcium, bicarbonate, phosphorus, total protein, albumin, glucose, uric acid will be measured according to the assessment schedule in [Table 8-1](#). If a given test is not available locally, this should be documented on the eCRF.

[figure not shown]
Additional markers of inflammation: CRP, ferritin, and d-dimer should be collected in accordance with [Table 8-1](#).

In the case where a laboratory range is not specified by the protocol, but a value is outside the reference range for the laboratory at screening and/or initial baseline, a decision regarding whether the result is of clinical significance or not shall be made by the Investigator (in consultation with the sponsor) and shall be based, in part, upon the nature and degree of the observed abnormality. In all cases, the Investigator must document in the source documents, the clinical considerations (i.e., result was/was not clinically significant and/or medically relevant) in allowing or disallowing the participant to continue in the study.

All patients with laboratory tests containing clinically significant abnormalities should be followed until the values return to within the normal ranges or until a clinical explanation is identified, even after study medication has discontinued.

#### **8.4.2 Physical exam**

A complete physical examination will be performed for baseline measurement at the time point defined in [Table 8-1](#). It will include the examination of general appearance, skin, neck (including thyroid), eyes, ears, nose, throat, lungs, heart, abdomen, back, lymph nodes,

extremities, vascular and neurological. Then, for remaining time points, targeted physical examination, per investigator discretion, may be performed.

Information for all physical examinations must be included in the source documentation at the study site. Significant findings that are present prior to informed consent being granted must be included in the Relevant Medical History/Current Medical Conditions screen on the patient's eCRF. Significant findings made after informed consent is given which meet the definition of an Adverse Event must be recorded on the Adverse Event screen of the patient's eCRF.

#### **8.4.3 Height, weight**

Height in centimeters will be measured at the Screening visit as specified in the table of assessments ([Table 8-1](#)).

Body weight (to the nearest 0.1 kilogram in indoor clothing, but without shoes) will be measured at the Screening visit as specified in the table of assessments ([Table 8-1](#)).

#### **8.4.4 Electrocardiogram (ECG)**

An ECG will be taken locally as specified in the [Table 8-1](#)

The ECG should be recorded after 10 minutes of rest in the supine position to ensure a stable baseline.

Each ECG tracing should be labeled with study number, patient initials patient number, date and time, and filed in the study site source documents.

Clinically significant abnormalities should be recorded on the relevant section of the medical history/Current medical conditions/AE CRF /eCRF page as appropriate. If necessary, a cardiologist may be consulted.

#### **8.4.5 Pregnancy and assessments of fertility**

All women of child-bearing potential (except if already confirmed pregnant) will have a serum pregnancy test at Screening and urine or serum pregnancy test at subsequent designated visits ([Table 8-1](#)), if hospitalized. Pregnancy tests will be conducted at the local lab and documented in the source documents.

#### **8.4.6 Chest x-ray or CT scan**

Standard chest x-ray or CT scan will be performed for eligibility except for those who have had a valid x-ray or CT scan done within 5 days prior to randomization. The results must be known prior to randomization to determine the patient's eligibility for the study. Additional chest x-rays (or CT scan) will be performed, as needed.

Chest x-ray or CT scan results will be recorded in the CRF.

#### **8.4.7 Appropriateness of safety measurements**

[figure not shown]
[figure not shown]
The safety assessments selected are appropriate for this protocol which utilizes a marketed compound where the safety profile has been established. The assessments are relevant to the critical care setting and will enable determination of therapeutic response in this setting.

[figure not shown]
## **8.5 Additional assessments**

### **8.5.1 SARS-CoV-2 nasopharyngeal samples**

Viral load may be measured by assessment of nasopharyngeal swabs sent to the central lab at time points designated in the assessment schedule ([Table 8-1](#)). Nasopharyngeal swabs should be taken in both nostrils or in the same nostril throughout the trial (whenever possible).

Laboratory Manuals will be provided with detailed information on sample collection, handling, and shipment

## **9 Study discontinuation and completion**

### **9.1 Discontinuation and completion**

[figure not shown]
#### **9.1.1 Study treatment discontinuation and study discontinuation**

Discontinuation of study treatment for a participant occurs when study treatment is stopped earlier than the protocol planned duration and can be initiated by either the participant or the investigator.

The investigator must discontinue study treatment for a given participant if, he/she believes that continuation would negatively impact the participant's well-being.

Study treatment must be discontinued under the following circumstances

- Participant/guardian decision
- Use of prohibited treatment as per recommendations in the prohibited treatment section
- Any situation in which study participation might result in a safety risk to the participant
- Following emergency unblinding

- Emergence of adverse events that in the judgment of the investigator, taking into account the participant's overall status, prevent the participant from continuing participation in the study
- Any laboratory abnormalities that in the judgment of the investigator, taking into consideration the participant's overall status, prevents the participant from continuing participation in the study
- Severe hypersensitivity reaction occurs, including any of the following: anaphylaxis, fever, chills, urticaria, dyspnea, headache, myalgia, hypotension. Immediate interruption of the infusion to administer study treatment is required in such cases.

If discontinuation of study treatment occurs, the investigator should make a reasonable effort to understand the primary reason for the participant's premature discontinuation of study treatment and record this information.

Participants who discontinue study treatment or who decide they do not wish to participate in the study further should NOT be considered withdrawn from the study UNLESS they withdraw their consent (see 'Withdrawal of Informed Consent' section). **Where possible, they should return for the assessments indicated** in the Assessment Schedule. If they fail to return for these assessments for unknown reasons, every effort (e.g. telephone, e-mail, letter) should be made to contact the participant/pre-designated contact as specified in the lost to follow-up section. This contact should preferably be done according to the study visit schedule.

If the participant cannot or is unwilling to attend any visit(s), the site staff should maintain regular telephone contact with the participant, or with a person pre-designated by the participant. This telephone contact should preferably be done according to the study visit schedule.

After study treatment discontinuation, at a minimum, in abbreviated visits, the following data should be collected at clinic visits or via telephone/email contact:

- New / concomitant treatments
- Adverse Events / Serious Adverse Events

[figure not shown]
The investigator must also contact the IRT to register the participant's discontinuation from study treatment.

If discontinuation occurs because treatment code has been broken, please refer to Emergency breaking of treatment code section.

### 9.1.2 Withdrawal of informed consent

Participants may voluntarily withdraw consent to participate in the study for any reason at any time. Withdrawal of consent (WoC) occurs only when a participant:

- Does not want to participate in the study anymore,  
and
- Does not want any further visits or assessments  
and
- Does not want any further study related contacts

In this situation, the investigator should make a reasonable effort (e.g. telephone, e-mail, letter) to understand the primary reason for the participant's decision to withdraw his/her consent and record this information.

Where consent to the use of personal and coded data is not required, participant therefore cannot withdraw consent. They still retain the right to object to the further use of personal data.

Study treatment must be discontinued and no further assessments conducted, and the data that would have been collected at subsequent visits will be considered missing.

Further attempts to contact the participant are not allowed unless safety findings require communicating or follow-up.

All efforts should be made to complete the assessments prior to study discontinuation. A final evaluation at the time of the participant's study discontinuation should be made as detailed in the assessment table.

Novartis will continue to retain and use all research results (data) that have already been collected for the study evaluation.

### **9.1.3 Lost to follow-up**

For participants whose status is unclear because they fail to appear for study visits without stating an intention to discontinue or withdraw, the investigator must show "due diligence" by documenting in the source documents steps taken to contact the participant, e.g. dates of telephone calls, registered letters, etc. A participant should not be considered as lost to follow-up until due diligence has been completed or until the time point of his/her scheduled last study visit has passed.

### **9.1.4 Early study termination by the sponsor**

The study can be terminated by Novartis at any time.

Reasons for early termination:

[figure not shown]
Unexpected, significant, or unacceptable safety risk to participants enrolled in the study

Decision based on recommendations from the internal data monitoring committee (DMC) after review of safety and efficacy data

In taking the decision to terminate, Novartis will always consider participant welfare and safety. Should early termination be necessary, participants must be seen as soon as possible and treated as a prematurely withdrawn participant. The investigator may be informed of additional procedures to be followed in order to ensure that adequate consideration is given to the protection of the participant's interests. The investigator or sponsor depending on local regulation will be responsible for informing IRBs/IECs of the early termination of the trial.

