Other assessments	
[REDACTED]
 
Standard safety and laboratory assessment will be performed during hospital stay and outpatient visits after discharge from hospital (See Assessment Table).
 
In addition, CRS / [REDACTED]
 

• CRP

• Ferritin

 
[REDACTED]
 
[REDACTED]
 
[REDACTED]
 
Additional Laboratory measurements:
 

• Absolute neutrophil count

• Monocytes

• Lymphocytes

• Lactate dehydrogenase

• D-dimer levels

Data analysis	
An absolute increase of 15% survival without ever requiring invasive mechanical ventilation is considered a clinically meaningful benefit. A total sample size of 450 with 1:1 randomization ratio is planned for the study, which is expected to ensure at least 89% power for the primary analysis. Conditional on the rejection of null hypothesis in primary analysis, and if the true 4-week case fatality rate for the control arm is no less than 15%, there will be at least 70% power to prove if canakinumab leads to a 50% relative reduction in the risk of death.
 
The primary analysis will be performed after all patients complete Day 29 assessment or discontinue early from the study before Day 29. Final analysis will happen after all patients complete the study. The primary analysis follows a treatment policy strategy to estimate the difference and odds ratio between the response rates of canakinumab and control arms. Hypothesis testing will be performed based on the odds ratio estimated using a logistic regression model with study treatment, region and baseline

	
clinical status as covariates. The two-sided type I error will be controlled at 0.05.
 
Key secondary endpoint of 4-week case fatality rate (CFR) will be compared between the two treatment arms using a logistic regression model with study treatment, region and baseline clinical status as covariates. Using a hierarchical testing procedure for familywise 2-sided type I error control at 0.05, the hypothesis test in key secondary analysis will be performed if and only if the null hypothesis in the primary analysis is rejected.
 
Other secondary analyses will include descriptive summaries without hypothesis testing.
 
[REDACTED]
 
Safety summaries will be produced for regular DMC safety monitoring.

Key words	COVID-19 pneumonia, SARS-CoV-2, canakinumab

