#### **4.4 Purpose and timing of interim analyses/design adaptations**

Not Applicable.

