### 10.2.2 Data Monitoring Committee

This study will include an internal data monitoring committee (DMC) which will function independently of all other individuals associated with the conduct of this clinical trial, including the site investigators participating in the study. The DMC will assess at defined intervals the progress of a clinical trial, safety data, and critical efficacy variables and recommend to the sponsor whether to continue, modify, or terminate a trial.

Specific details regarding composition, responsibilities, data monitoring, and meeting frequency, and documentation of DMC reports, minutes, and recommendations will be described in a separate charter that is established with the DMC.

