## 12.6 Interim analyses

Summaries of safety data will be produced for DMC safety monitoring when needed.

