### 12.7.2 Secondary endpoint(s)

[figure not shown]
Using a hierarchical testing procedure for familywise 2-sided type I error control at 0.05, the hypothesis test in key secondary analysis on 4-week CFR will be performed if and only if null hypothesis in primary analysis is rejected. The conditional power for detecting a 50% drop of 4-week CFR are evaluated under different assumptions on control arm 4-week CFR.

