## 2.6 Analysis of the key secondary objective

The key secondary efficacy analysis is based on FAS. The inferential testing on the key secondary endpoint specified in this section will be performed if the null hypothesis of the primary endpoint is rejected with a two-sided testing with p-value less than 0.05. This testing procedure controls the overall two-sided type-I error rate to less than 0.05 within the study.

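### Does DMC access to efficacy data amount to an unplanned interim look that threatens the two-sided 0.05 level?

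*Protocol*

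**What the plan says.** Two places give the data monitoring committee (DMC) a role that reaches efficacy. Protocol 9.1.4 lists two grounds for early termination. One is an unacceptable safety risk. The other is a "Decision based on recommendations from the internal data monitoring committee (DMC) after review of safety and efficacy data". Protocol 10.2.2 has the committee assess "safety data, and critical efficacy variables and recommend to the sponsor whether to continue, modify, or terminate a trial". Protocol 6.4 adds that the committee and an independent statistician and programmer may obtain treatment codes to produce and review unblinded interim results.

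The sections that would hold an interim analysis plan say something narrower. Protocol 4.4 covers interim analyses and design adaptations, and its whole entry is "Not Applicable". Protocol 12.6 reads: "Summaries of safety data will be produced for DMC safety monitoring when needed". SAP 2.10 repeats that sentence. Protocol 4.5 describes a committee that reviews safety data, and Protocol 3, Protocol 12 and SAP 1.1 describe its work as safety monitoring.

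The error-rate statements assume a single efficacy analysis. The protocol summary says "The two-sided type I error will be controlled at 0.05". Protocol 12.7.2 describes the order of testing: "Using a hierarchical testing procedure for familywise 2-sided type I error control at 0.05". SAP 2.6 says of that order: "This testing procedure controls the overall two-sided type-I error rate to less than 0.05 within the study". Protocol 12 sets the primary analysis after every patient has finished Day 29 or left the study before it.

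**The concern.** Safety risk already has its own line in Protocol 9.1.4, so the second ground reads as something wider, possibly including a stop because the drug looks effective. If unblinded efficacy results could end the trial for benefit, the Day 29 test would not be the only chance to claim success, and a plain 0.05 at that test would not hold the overall error at 0.05.

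The text also seems to leave a path to a test after such a stop. Protocol 9.1.4 says that on early termination "participants must be seen as soon as possible and treated as a prematurely withdrawn participant". Protocol 12 starts the primary analysis once all patients have reached Day 29 or discontinued, so the condition would then be met on a smaller sample. No level other than 0.05 is given, and a significant primary result would open the test of the 4-week case fatality rate on fewer patients than planned.

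The credibility of both confirmatory claims would be at stake. The plan states that its blinded sample size re-evaluation does not inflate type I error, but gives no such assurance for unblinded DMC review.

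**Working it through.** **Step 1. Is the stated power that of a single test at 0.05?** Inputs from Protocol 12.7.1 and Table 12-1: 225 patients per arm, two-sided alpha 0.05, a 15-point difference. With p̄ the mean of the two rates:

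se0 = √(2·p̄·(1−p̄)/225), se1 = √([p1(1−p1)+p2(1−p2)]/225), power = Φ((|p2−p1| − 1.96·se0)/se1).

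For 40% against 55%: p̄ = 0.475, se0 = 0.0471, se1 = 0.0465, so (0.15 − 1.96 × 0.0471)/0.0465 ≈ 1.24 and power = 89.3%.

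| Control | Canakinumab | Computed | Stated |
|---|---|---|---|
| 50% | 65% | 89.9% | 89% |
| 40% | 55% | 89.3% | 89% |
| 30% | 45% | 91.0% | 90% |
| 20% | 35% | 94.8% | 94% |

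The stated figures are reproduced to within about one point by one final test at the full 0.05. No alpha has been set aside for an earlier look.

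**Step 2. What would an interim claim of benefit need, and is it in the plan?**

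| Element | In the visible protocol and SAP |
|---|---|
| Interim efficacy hypothesis or test | None; Protocol 4.4, Protocol 12.6 and SAP 2.10 point the other way |
| Stopping boundary or alpha allotted to a look | None |
| Efficacy output for the DMC | None; safety summaries only |
| Statement that a DMC stop would count as success | None |
| Unblinded design adaptation | None; the only adaptation described is the blinded sample size re-evaluation |

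Protocol 10.2.2 sits under the heading for additional safety monitoring, and its sentence is general in form. A recommendation to modify the protocol would still need a written, approved amendment under Protocol 14.1.

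**Step 3. Why would a safety committee see efficacy data at all?** In this trial the two overlap. Death is score 8 on the ordinal scale and makes a patient a non-responder on the primary endpoint. It is also the event that Protocol 3 has the committee monitor in real time. Mortality cannot be reviewed for safety without seeing part of the efficacy endpoint, and harm cannot be weighed without some view of benefit. Stopping for harm or futility does not raise the rate of false claims of benefit.

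**Step 4. How large would the problem be if the plan did allow a stop for benefit?** The documents give no looks and no rule, so both are assumptions here: K equally spaced analyses including the final one, with corr(Z_i, Z_j) = √(i/j) for i<j under the null. A false claim of benefit is any upward crossing:

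P(false benefit) = 1 − P(Z_1<c_1, …, Z_K<c_K).

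| Rule | K=2 | K=3 | K=5 |
|---|---|---|---|
| Every analysis at two-sided 0.05 (c = 1.96 throughout) | 4.2% | 5.4% | 7.1% |
| Interim p<0.001 (c = 3.29), final 1.96 | 2.5% | 2.5% | 2.6% |
| One final test only, as planned | 2.5% | 2.5% | 2.5% |

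The benefit direction is the relevant one, because the worry is a stop for benefit. Figures of 8.3%, 10.7% and 14.2%, which the first rule gives when crossings in either direction count, would overstate that risk.

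**The case for a change.** The strongest case for a change runs as follows. The sections describe the committee differently. In Protocol 9.1.4 and 10.2.2 it weighs efficacy and can recommend termination, while in Protocol 4.4, 4.5 and 12.6 and SAP 2.10 it receives safety summaries. Safety risk is a separate ground in 9.1.4, so the second ground must add something. The amendment requirement restrains modification but not termination, which the sponsor may decide at any time. The claim of overall error control appears in the protocol and SAP, so a reader should not need an unseen charter to trust it. One sentence ruling out a stop for benefit would cost no patients, alpha or power.

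Part of this stands. The wording is uneven, no visible sentence expressly excludes a stop for benefit, and the sentence would be cheap. But the second ground need not mean a claim of success: a recommendation made on the balance of benefit and risk, or for futility, fits the words equally well. Protocol 4.4 already says that no interim analysis or adaptation is planned, so the added sentence would repeat what is there. The detailed rules are deferred to a charter (Protocol 6.4 and 10.2.2) and a separate DMC analysis plan (SAP 1.1), and their absence from the public documents does not show that a rule is missing.

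**Conclusion.** The concern does not call for a change. The sections are not worded alike, but following them does not produce a second efficacy test. The plan has one primary test at two-sided 0.05 after Day 29, then the case fatality test if the primary succeeds, and on that reading the error rate is the stated 0.05 and the stated power holds. No inflation is shown. The rise to between 4.2% and 7.1% false claims of benefit requires repeated testing at unadjusted 0.05, which nothing in the documents suggests. Under a strict p<0.001 rule the rate would hardly move from 2.5%.

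This rests on taking Protocol 4.4 at its word and on reading the DMC's efficacy access as context for weighing benefit against risk. The charter and the DMC analysis plan were not available, and some statistical text is redacted. If either DMC document gave the committee a rule for stopping on benefit, the conclusion would have to be revisited. On the visible text this is general committee wording that an analyst would read correctly, and the Day 29 analysis would be run the same way with or without a clarifying sentence.

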## **9.2 Study completion and post-study treatment**

Study completion is defined as when the last participant finishes their Study Completion visit and any repeat assessments associated with this visit have been documented and followed-up appropriately by the Investigator or, in the event of an early study termination decision, the date of that decision.

Continuing care should be provided by the investigator and/or referring physician based on participant availability for follow-up.

